6.6.6 Participant transfers

If a participant moves from the area making continued follow up at their consenting centre inappropriate, every effort should be made for them to be followed at another participating trial centre and / or remotely.

6.6.6.1 Transfer to another participating centre

Written consent should be taken at the new centre and then a copy of the participant's CRFs should be provided to the new centre. Responsibility for the participant remains with the original consenting centre until the new consent process is complete.

6.6.6.2 Transfer to a non-participating centre

Follow-up and data collection may continue remotely. CGM sensors may still be provided if this is in the best interests of the participant, and CGM data will continue to be collected remotely for the purposes of the trial. The original consenting centre should obtain outcome data from the new centre where possible. The participant's clinical care is the responsibility of the new centre.

6.6.6.3 Delivery at non-participating centres

Participants who deliver their babies at another centre or whose babies are in NICU at another centre should be followed up by the original consenting centre.

6.6.7 Loss to follow-up

Participants will be in contact with the clinical care team at 4-weekly intervals during the trial, or more frequently if clinically indicated.

6.6.8 Trial closure

The end of the trial is defined as 6 months following the last follow-up visit of the last patient, to allow for data entry and data cleaning activities to be completed.

6.7 Sample size

Assuming an anticipated neonatal care outcome incidence of 42.2% in the standard care group, based on national audit data (2, 5), a sample size of 422 would show a reduction from 42.2 to 26.0% at two-

sided 5% significance with 90% power and an assumed drop-out of 10%. An absolute reduction of 16.2% or odds ratio of 0.48 for neonatal unit admissions is based on our previous RCT data (28). The neonatal effect size in our earlier RCT (40) was higher (0.36)⁴⁰, so the most conservative estimate was chosen. A slightly smaller sample of 406 is required for the neonatal composite of neonatal admissions and death.

For the primary maternal outcome of CGM Time-in-Range (TIR) from 20 weeks until 38 weeks or delivery, 188 participants are required to detect a clinically relevant 10% increase from 60 to 70% TIR with 90% power. Using a sample size of 422 (380 analysable 14-day CGM profiles), provides 90% power to detect a CGM TIR difference of 6.65% which is deemed to be a clinically important difference. The expected maternal TIR outcome of 60% TIR (SD 20%) in the control group is based on limited EOT2D data (40-42).

The trial is powered on the neonatal unit admission outcome (involving separation of the newborn from their mother). A superiority analysis of the composite endpoint will be performed.

Sample size									
Outcome	Power	Significance	Control	Interven-	Difference	SD	Drop-	Total	
				tion			outs		
Neonatal	90%	5% (2-	42.2%	26.0%	OR 0.48	N/A	10%	422	
care		sided)			Absolute 16.2%				
Neonatal	90%	5% (2-	48.8%	31.7%	OR 0.48	N/A	10%	406	
composite		sided)			Absolute 17.2%				
CGM TIR*	90%	5% (2-	60.0%	70.0%	10.0%	20%	10%	188	
		sided)							

Table 1: Sample size estimations

*A sample size of 422 provides 90% power to detect a CGM TIR difference of 6.6% which is clinically important

6.8 Assignment of intervention

6.8.1 Allocation

6.8.1.1 Sequence generation

Eligible participants will be randomised via a web-based randomisation system hosted by the Norwich Clinical Trials Unit (University of East Anglia (UEA)). Women will be allocated on a 1:1 basis to either the intervention arm (real time CGM) or control arm (routine clinical care). Randomisation is stratified by site.

6.8.1.2 Allocation concealment mechanism

The allocation is computer generated so will not be known prior to the participant being randomised. The patient will be allocated a participant number at time of consent. When all pre-designated questions have been completed in the CRF, the research staff will have access to the randomisation process for that participant. The treatment allocation will be revealed and linked to that participant number. Allocation is concealed prior to randomisation to prevent treatment bias.

6.8.1.3 Allocation implementation

Eligible participants will be randomised using central randomisation software using computer generated blocks of random sizes.

6.8.2 Blinding

This is an unblinded trial. Both participants and their clinical care team will be aware of the allocation.

6.9 Data collection, management and analysis

6.9.1 Data collection methods

Each participant will be given a unique trial Participant Identification Number (PID) at the recruitment visit. Data will be collected from this point at the time-points indicated in section 6.6.

The preferred method of data collection is direct online entry of data onto the central database, stored on servers based at NCTU, by members of the PROTECT trial team working within each research site. Data may be entered onto paper Case Record Forms (CRFs) prior to entry onto the database (but this is not an essential step). Staff will receive training on data collection and use of the online system.

Safety data and other data requiring expedited reporting will be reported directly to NCTU via email using supplied paper CRFs in accordance with section 7.

CGM data will be collected via web-based diabetes management software intended for use with the FreeStyle Libre CGM system (Abbott Diabetes Care, Inc.). Digital glucose data from non-study glucose monitoring systems may be collected in linked-anonymised form.

Data collection, data entry and queries raised will be conducted in line with the NCTU and trial specific Data Management Standard Operating Procedure.

Clinical trial team members will receive trial protocol training. All data will be handled in accordance with the General Data Protection Regulation (GDPR) (EU) 2016/679 and the Data Protection Act 2018.

6.10.2 Data management

Data will be entered under the participant's PID onto the central database stored on the servers based at NCTU. Access to the database will be via unique, individually assigned (i.e. not generic) usernames and passwords, and only accessible to members of the PROTECT trial team at NCTU, and external regulators if requested. The servers are protected by firewalls and are patched and maintained according to best practice. The physical location of the servers is protected physically and environmentally in accordance with University of East Anglia's General Information Security Policy 3 (GISP3: Physical and environmental security).

The database and associated code have been developed by NCTU Data Management, in conjunction with the PROTECT trial team. The database software provides a number of features to help maintain data quality, including maintaining an audit trail, allowing custom validations on all data, allowing users to raise data query requests, and search facilities to identify validation failure/ missing data.

Data will be shared with the Jaeb Center for Health Research (JCHR) in accordance with a data sharing agreement, in order for them to carry out statistical analyses.

IRAS Project ID: 331906

After completion of the trial the database will be retained on the servers of NCTU for on-going analysis of secondary outcomes. The database will be archived a minimum of one year after the publication of primary outcome.

Identification, screening and enrolment logs, linking participant identifiable data to the pseudoanonymised PID, will be held locally by the trial site. This will either be held in written form in a locked filing cabinet or electronically in password protected form on hospital computers. After completion of the trial the identification, screening and enrolment logs will be stored securely by the sites for 10 years unless otherwise advised by NCTU.

6.10.3 Non-adherence and non-retention

Every effort will be made to record the reasons for non-adherence (e.g. discontinuation of intervention due to harms or lack of efficacy) and non-retention (i.e. consent withdrawn; loss to follow up) as this information can influence the handling of missing data and interpretation of results.

6.10.4 Statistical methods

6.10.4.1 Primary outcome analysis

Maternal glucose:

The primary analysis will evaluate the change in the time spent in the target glucose range (CGM TIR 3.5-7.8 mmol/L) between the intervention and control arm between 20 weeks' gestation and 38 weeks or until delivery (if delivered earlier), based on 4 x 14-day CGM assessments, at 20-22, 28-30, 32-34 and 36-38 weeks. The median gestation of delivery in T2D pregnancy is 38 weeks. A linear mixed effects regression model will be fit with CGM TIR from 20 weeks' gestation until delivery as the dependent variable adjusting for baseline CGM TIR, and subject as random effects. A point estimate, 95% confidence interval and p-value will be reported for the treatment effect based on the linear regression model. Residual values will be examined for an approximate normal distribution. If values are highly skewed, then a transformation or robust statistical methods will be used instead.

Neonatal outcomes:

The primary neonatal outcome is a composite of neonatal unit admission or death in line with section 6.10.4.3.

6.10.4.2 Secondary outcome analyses

The same approaches as in 6.10.4.1 will be applied to secondary CGM metrics including:

- Mean CGM glucose
- Glucose management indicator (GMI)
- Time above range (TAR >6.7 & >7.8 mmol/L) and time below range (<3.5 & <3.0 mmol/L)

For all above mentioned secondary analyses, the false discovery rate will be controlled using an appropriate statistical procedure. Measures of glucose variability (SD and CV) have skewed distributions and will be compared between groups using a logarithmic transformation.

The analysis of HbA1c data will use the data collected at baseline, 28, 32 and 36 weeks in a longitudinal analysis over the entire study period. The planned linear mixed effects model will include baseline HbA1c as the dependent variable. This analysis focuses on whether the slope of change in HbA1c over the three follow-up time points is different between the treatment groups. The estimated correlation matrix between the intercept and slope of the random effects will be examined to assess whether larger rates of decreases in HbA1c are associated with higher initial values.

6.10.4.3 Dichotomous outcomes

For severe hypoglycaemia / hyperosmolar hyperglycaemic state (HHS) / DKA episodes, and rarer outcomes such as birth defect / stillbirth / neonatal deaths, proportions will be compared between treatment groups using Fisher's exact test. For any events which occur in at least 30 participants, logistic regression will be used to compare treatment groups and explore other factors contributing to obstetric and neonatal risks.

- Maternal target glucose attainment (HbA1c <43 mmol/mol, CGM time-in-range international consensus targets)
- Severe hypoglycaemia, hyperosmolar hyperglycaemic state, and diabetic ketoacidosis episodes
- Incident gestational hypertension or preeclampsia

- Pregnancy loss: miscarriage, congenital anomaly, stillbirth, neonatal death (death ≤28 days of life)
- Preterm birth (<37 weeks and early preterm <34 weeks)
- Birth injury (spinal cord injury, clavicular, skull or long bone fracture, shoulder dystocia, nerve palsy, subdural or intracerebral haemorrhage confirmed by computerized tomography (CT) or magnetic resonance imaging (MRI) scan, hypoxic ischaemic encephalopathy)
- Birth weight >90th centile using customized centiles
- Birth weight <10th centile using customized centiles
- Mode of delivery
- Infant feeding

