2.3 Structured trial summary

Primary Registry and Trial Identifying Number	ISRCTN12804317
Date of Registration	23/10/2023
Secondary Identifying Numbers	IRAS Project ID: 331906
Monetary or Material Support	NIHR Health Technology Assessment (HTA) Programme: NIHR150958. Devices supplied by Abbott Diabetes Care, Inc.
Sponsor	University of East Anglia
Contact for Public Queries	[contact]
Contacts for Scientific Queries	[name] [name] MBBChBAO, FRACP, MD Honorary Consultant Physician, Norfolk and Norwich University Hospital NHS Foundation Trust / Professor of Medicine (Diabetes and Antenatal Care) [contact] Email: [contact] Address: [name] [name] BM BS MD FRCP Professor of Medicine (Diabetes and Maternal Health), Leeds Institute of Cardiovascular and Metabolic Medicine, University of Leeds / Leeds Centre for Diabetes and Endocrinology, Leeds Teaching Hospitals NHS Trust [contact] Email: [contact] Address: [name]
Short Title or Acronym	PROTECT – PR egnancy O utcomes using continuous glucose monitoring TEC hnology in pregnant women with early-onset T ype 2 diabetes
Scientific Title	A multicentre randomised controlled trial of the clinical and cost- effectiveness of using continuous glucose monitoring (CGM) in pregnant women with early-onset type 2 diabetes
Countries of Recruitment	United Kingdom
Health Condition Studied	Early-onset type 2 diabetes during pregnancy

Intervention	Intervention arm: A Real-Time Continuous Glucose Monitoring (CGM) system
	Control arm : Standard clinical care, which may be finger-prick Self- Monitoring Blood Glucose (SMBG) or continuous glucose monitoring.
Inclusion and Exclusion Criteria	 Inclusion criteria: Type 2 diabetes (T2D) 16 years of age or over Confirmed pregnancy HbA1c of ≥43 mmol/mol (6.1%) in pregnancy (prior to randomisation) Willingness to use the study devices throughout the trial Able to provide informed consent 4 days (aiming for ≥96 hours) of baseline CGM data before randomisation at no later than 16+0 weeks' gestation. In cases where 72-96 hours of CGM data is available, inclusion may be approved by the NCTU team. Exclusion criteria: Non-type 2 diabetes Women with chronic kidney disease (CKD) grade 4 or 5 (GFR <30ml/min)

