Importantly, MATERNAL GLUCOSE is the KEY MODIFIABLE RISK FACTOR for neonatal morbidity and death (2, 5). National audit data reported 565 serious adverse outcomes in EOT2D mothers with above-target glucose compared to 105 in T2D mothers with in-target glucose levels. Serious neonatal morbidity (neonatal unit admissions >24 hour) and mortality are significantly reduced in babies of mothers who achieved target glucose levels (HbA1c <43 mmol/mol) after 24 weeks' gestation (5).

Neonatal care admissions separate mothers and babies, with immediate and longer-term consequences for maternal wellbeing, mother-baby bonding, and infant feeding. The average neonatal care admission in EOT2D pregnancy is 5 days, which at £9,463.70 (£1,892.74 daily) is a major cost burden for the NHS (9).

WHY IS THIS RESEARCH IMPORTANT NOW?

1) Understanding whether diabetes technology can improve pregnancy outcomes was the number one James Lind Alliance (JLA) Priority Setting Partnership (PSP) priority for diabetes pregnancy research(10). Listening to the priorities of pregnant women is particularly pertinent following the Ockenden report, where many women, especially from ethnic minorities and poorer communities reported poor experiences...*I felt frightened and not listened to*..." (9, 11, 12).

2) The burden of EOT2D pregnancy is high(2), and rapidly increasing with gestational diabetes (GDM) affecting one in seven women, half of whom will develop EOT2D within 5 years (7).

3) Nearly ONE in TWO BABIES born to mothers with EOT2D have serious health complications (birth defects, neonatal care admissions or death) with major impacts for women, families and the NHS(2, 5). We know that many adverse outcomes are potentially preventable by improving maternal glucose (2, 3, 13).

4) There are stark healthcare inequalities in access to diabetes technology. Currently, <15% of mothers with EOT2D (ethnically diverse, higher BMI, more deprived) are offered continuous glucose monitoring (CGM) compared to >90% of mothers with T1D (predominantly white, lower BMI, more affluent). Recent NICE guidance (31/03/22) highlighted the urgent need to address health inequalities in CGM access. Addressing inequalities by bringing high quality research to under-served communities is also a key NIHR priority.

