6.3.1.1 Participant inclusion criteria

- 1. Type 2 diabetes (T2D)
- 2. 16 years of age or over
- 3. Confirmed pregnancy
- 4. HbA1c of \geq 43 mmol/mol (6.1%) in pregnancy (prior to randomisation)
- 5. Willingness to use the study devices throughout the trial
- 6. Able to provide informed consent
- 4 days (aiming for ≥96 hours) of baseline CGM data before randomisation at no later than 16+0 weeks' gestation. In cases where 72-96 hours of CGM data is available, inclusion may be approved by the NCTU team.

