6.6.1.6 Procedures following training

Following training, participants in the intervention arm will proceed to use CGM throughout pregnancy and delivery. Participants in the control arm will continue to use current methods of glucose monitoring and will keep a paper logbook or electronic diary of their glucose values, which will be reviewed as per routine care. Participants using continuous glucose monitoring will share their sensor glucose data directly with the trial team. Participants in the control arm will have masked study CGM sensors applied at 20, 28, 32 and 36 weeks' gestation to collect comparable outcome data (those using non-study continuous glucose monitoring will be asked to wear a masked study sensor alongside their own to allow comparable data to be collected).

Glucose targets for both groups are as follows:

- fasting glucose levels 3.5-5.3 mmol/L
- 1 hour post-prandial <7.8 mmol/L
- 2 hours post-prandial <6.7 mmol/L
- HbA1c <43 mmol/mol

Treatment should be adjusted by women and local HCP teams using metformin and/or insulin if glucose levels are out of range on three or more occasions and dietary intervention is unlikely to be adequate for optimal maternal glucose levels.

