6.6.1.7 Study visits

Follow up visits will be every 4 weeks at ~16/40, 20/40, 24/40, 28/40, 32/40, 36/40 (+/- 2 weeks). It is expected that the majority of ongoing study visits will align with routine NHS antenatal clinic visits however virtual study visits (e.g., using phone or video calls) will be offered if appropriate, and data from community appointments may be used if needed.

At these visits the following data will be recorded on the study database:

- Weight
- Blood pressure
- Glucose monitoring method(s), frequency of glucose testing
- Insulin delivery method(s), dose and type, if relevant
- Other diabetes treatment

• Adverse events of special interest

In addition to the data collected above (6.6.1.7), the following will be performed at key visits:

- Masked CGM for control group participants (14 days data collection) at 20, 28, 32, and 36 weeks' gestation
- Blood collection for HbA1c at 28, 32, and 36 weeks' gestation
- Follow-up questionnaires at 32 weeks' gestation

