6.10.4.7 Statistical analysis

A detailed statistical analysis plan (SAP) for the primary and secondary outcomes will be written and approved before database lock and commencement of data analyses. We will report data in line with the Consolidated Standards of Reporting Trials (CONSORT) statement showing attrition rates and loss to follow-up. Analyses will be conducted using the intention-to-treat principle, incorporating data from all participants according to randomised group. Every effort will be made to follow up participants for outcome assessments including those who withdraw from trial interventions.

Descriptive statistics within each randomised group will be presented for baseline values. These will include counts and percentages for binary and categorical variables, and means and standard deviations (SD), or medians with lower and upper quartiles (IQR), for continuous variables, along with minimum and maximum values and counts of missing values. There will be no tests of statistical significance or confidence intervals for differences between randomised groups on baseline variables.

Treatment effects on biomedical outcomes will be estimated using linear mixed models fitted to outcome variables, adjusted for individual baseline where available, and study site as a random factor to account for potential between site differences. Where variables are measured at multiple timepoints, mixed linear models will be used to utilize data at all time points. Treatment effect on the primary neonatal endpoint will be expressed as an odds ratio with 95% CI estimated from a logistic regression model. For the primary maternal endpoint, the comparison between the two treatment arms is based on a general mixed effects regression model. The two primary endpoints will be treated as fixed effects in mixed models.

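### The logistic comparison of glucose target attainment names no baseline term, which gives up power that baseline HbA1c, already collected, would supply (minor)

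*Protocol*

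**What the plan says.** - **Outcome.** Protocol 6.10.4.3 (Dichotomous outcomes) lists "Maternal target glucose attainment (HbA1c <43 mmol/mol, CGM time-in-range international consensus targets".
- **Test.** The same section says: "For any events which occur in at least 30 participants, logistic regression will be used to compare treatment groups". It adds that the regression will also look for other contributors to obstetric and neonatal risk, but it names no baseline covariate for the arm comparison. Fisher's exact test is kept for severe glycaemic episodes and rarer outcomes.
- **General adjustment rule.** Section 6.10.4.7 (Statistical analysis) says: "Treatment effects on biomedical outcomes will be estimated using linear mixed models fitted to outcome variables, adjusted for individual baseline where available". The logistic model for the primary neonatal endpoint is described later in that paragraph without a baseline term.
- **Entry.** Section 2.3 requires "HbA1c of ≥43 mmol/mol (6.1%) in pregnancy (prior to randomisation", and section 6.3.1.1 repeats it.
- **Where the cut-off comes from.** Section 6.6.1.6 sets "HbA1c <43 mmol/mol" as a glucose target in both arms. Section 5.1 reports lower neonatal morbidity and mortality in "babies of mothers who achieved target glucose levels (HbA1c <43 mmol/mol) after 24 weeks' gestation".
- **Follow-up values.** Section 6.6.1.7 schedules "Blood collection for HbA1c at 28, 32, and 36 weeks".

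**The concern.** Each woman's chance of ending below 43 mmol/mol depends heavily on where she started: one entering at 44 is far closer to target than one entering at 80. A logistic model with treatment alone leaves that spread unexplained. Randomisation keeps the comparison fair, but part of the available power is given up.

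The text does not secure the adjustment elsewhere. The rule in 6.10.4.7 is tied to linear mixed models. The primary CGM model in 6.10.4.1 adjusts for baseline TIR, but that is a linear model of a continuous outcome. The longitudinal HbA1c model in 6.10.4.2 places baseline HbA1c on the outcome side, so it supplies no covariate rule either. An analyst following 6.10.4.3 literally would fit treatment only.

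At stake is the precision of a secondary outcome. Neither primary outcome and no part of the sample size is affected.

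**Working it through.** **1. Number analysed.** The protocol states no power for HbA1c attainment, so there is no figure of its own to reproduce on this point. The size of the comparison can be checked from section 6.7: 422 × 0.90 = 379.8, or 380 women, 190 per arm. With the stated SD of 20, the detectable TIR difference at 90% power is 20 × (1.960 + 1.282) × √(2/190) = 6.65, which matches section 6.7. I use 190 per arm below.

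**2. Which test applies.** Thirty events among 380 women is 30/380 = 7.9%. In the worked single-visit scenarios below for which arm rates are shown, attainment is 18% or more in the control arm, so the logistic model applies and Fisher's test does not.

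**3. Gain from adding baseline HbA1c (assumptions throughout).** The protocol gives no HbA1c distribution, within-person SD or expected HbA1c effect.

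*Set A.* True baseline normal with the mean/SD shown; entry if the observed value is at least 43; measurement SD 1.5; control fall 8, extra fall with CGM 4, SD of change 5 mmol/mol; 800 simulated trials.

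| Baseline mean/SD | Attainment, control vs CGM | Power, treatment only | Power with baseline HbA1c | Gain (points) |
|---|---|---|---|---|
| 50/8 | 43.7% vs 62.8% | 0.968 | 0.996 | 3 |
| 55/10 | 28.0% vs 43.5% | 0.875 | 0.983 | 11 |
| 60/14 | 18.3% vs 28.9% | 0.695 | 0.950 | 26 |

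Hand check of the middle row, treatment only:
- log odds ratio = ln[(0.435/0.565)/(0.280/0.720)] = 0.683
- SE = √[1/(190 × 0.280 × 0.720) + 1/(190 × 0.435 × 0.565)] = 0.218
- z = 0.683/0.218 = 3.13
- power = Φ(3.13 − 1.96) = 0.88, which agrees with the simulation

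With no true effect, rejection rates were 4.9% to 6.3% without baseline and 4.1% to 5.6% with it. The Monte Carlo SE is √(0.05 × 0.95/800) = 0.8 points, so both are consistent with 5%.

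*Set B.* Log-normal baseline; measurement SD 2.5; follow-up shrunk halfway towards 41 with residual SD 4; extra CGM effect 2 mmol/mol. Single-visit power rose as follows:
- 48/9: from 77% to 85% (8 points)
- 52/12: from 65% to 75% (10 points)
- 56/14: from 56% to 69% (13 points)

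A further set of assumed distributions at 190 per arm gave about 6 to 16 points, which I take as the working range. The gain grows as baseline spread grows and as follow-up HbA1c tracks baseline more closely.

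**4. Does the shared cut-off dilute the comparison?** In Set A, with measurement SD from 1 to 3, I compared the arm difference using error-free HbA1c with that using a single noisy value:
- 55/10, SD 1.5: 15.7 to 15.5 points
- worst case (50/8, SD 3): 19.3 to 18.3 points
- overall: a shrinkage of 0.0 to 1.0 points on differences of 11 to 19, and at most about 3 points of power

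A separate simulation gave 0.1 to 1.2 points. Requiring a second confirming value changed power by only −0.2 to +1.1 points.

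**5. CGM attainment.** The same reasoning applies with baseline TIR as the covariate. I did not quantify that gain.

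**The case against.** **Covariates are SAP detail.** Section 6.10.4.7 announces a detailed SAP, the adjustment rule there can be read broadly, and 6.10.4.3 never says the logistic model is unadjusted. Most of this stands, and it is why the point is minor. What remains is that the protocol does fix a model for this outcome, and its only general adjustment rule is attached to a different class of model.

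**The power figures rest on invented inputs.** True. The direction is the same in every set, but the size is not known from the documents.

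**HbA1c is also analysed on its continuous scale** (6.10.4.2 and 6.10.4.4), so little hangs on the dichotomy. That also stands.

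**Stronger readings that a reader might infer.**
- *Women who enter just above 43 become responders through measurement noise, so the comparison is compromised.* With no true change in anyone, noise alone would put 0.9% to 7.1% of entrants below 43 at one visit under the Set A baselines. This happens equally in both arms, creates no bias, and costs at most about one percentage point of the difference (step 4).
- *The shared threshold is a design error.* It is the protocol's own treatment target and the level it links to neonatal outcome. Every woman enters off target, and the outcome asks whether she reaches it.
- *The unadjusted analysis treats women entering at 44 and at 80 as equally likely to reach target.* A randomised comparison of proportions assumes no such thing.
- *The plan needs a confirmation rule or must name the deciding visit now.* Confirmation gains almost nothing, and the visit can properly be named in the SAP.

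**Conclusion.** The point holds as a minor improvement. Section 6.10.4.3 sets a logistic comparison of target attainment with no baseline term, and the wording of 6.10.4.7 does not clearly bring one in. The planned comparison is valid, with no bias and a type I error near 5%, but it is less powerful than the collected data allow. The loss is about 6 to 16 percentage points of power at 190 per arm, and 3 to 26 across the widest set of assumptions examined. These figures depend on assumed HbA1c distributions, effects and tracking, because the protocol supplies none. The gain comes from explaining the spread in baseline HbA1c, not from removing noise responders, so it would apply whatever the entry threshold. The documents do not support a claim of material dilution or of a faulty cut-off.

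**What to change.** Add to section 6.10.4.3 that the logistic model for HbA1c target attainment includes continuous baseline HbA1c, and that the model for CGM target attainment includes baseline TIR. Leave the 43 mmol/mol threshold as it is and add no confirmation rule. Name the deciding visit in the SAP.

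The cost is a sentence of wording. Both covariates should be available for every randomised woman, because the inclusion criteria require an HbA1c before randomisation and baseline CGM data. One consequence to note: the adjusted odds ratio is conditional on baseline and will generally lie further from 1 than the unadjusted one, so the simple attainment percentages by arm should be reported beside it.
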